**Table 4 - Analysis Time Windows**

Phase	Time point	Time Window
Pre-Treatment	Baseline	Last value prior to start of study treatment (i.e. $\leq$ study day 1)
Treatment Weeks		Study day during treatment period (Study day 1 = first treatment day)
	4 (day 29)	15 - 42
	8 (day 57)	43 - 70
	12 (day 85)	71 - 98
	16 (day 113)	99 - 126
EoT	Actual EoT	Study day of last dose (28 days prior to EoT - 14 days post EoT)
Post Treatment	4 weeks (day 29 post EoT)	15 – 56 post EoT
	12 weeks (day 85 post EoT)	57 – 112 post EoT
	24 weeks (day 169 post EoT)	141 – 196 post EoT

Mean changes from baseline to each post-baseline visit will be summarized descriptively.

Laboratory data values collected during the treatment period will be categorized as low, normal, or high based on reference ranges used in this study. The number and percent of patients who experience post-baseline shifts during treatment in clinical laboratory values from low/normal to high and high/normal to low based on the reference range will be summarized.

Additional details of the analyses of clinical laboratory data will be specified in the SAP.

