4.2.6.4 Co-morbidities and co-infections

A summary table will present the absolute and relative frequencies of HCV co-infections, CHC related comorbidities and other co-morbidities, in more detail:

- HCV Co-infections
 - Human immunodeficiency virus (HIV)
 - Hepatitis B virus (HBV)
 - Tuberculosis
 - Schistosomiasis
- Liver and/ or CHC related co-morbidities
 - Liver transplantation
 - Hepatocellular carcinoma
 - Steatosis (non-alcoholic)
 - Alcoholic liver disease
 - Primary biliary cirrhosis

- Auto-immune hepatitis
 - Wilson disease
 - Cryoglobulinemia
 - Porphyria cutanea tarda (PCT)
 - Auto-immune skin disease
- Other co-morbidities
 - Kidney transplant
 - Chronic kidney disease (Mild, Moderate, Severe, Currently on dialysis, Currently not on dialysis)
 - Psychiatric disorders (Depression, Bipolar disorder, Schizophrenia, Personality disorder)
 - Diabetes mellitus (Type 1, Type 2)
 - Insulin resistance
 - Metabolic syndrome
 - Lipid disorder
 - Hyperthyroidism
 - Hypothyroidism
 - Cardiovascular disease (Myocardial infarction, Angina pectoris, Hypertension, Stroke)
 - Immunologically mediated disease
 - Hemophilia
 - Thalassemia
 - Sickle cell anemia
 - V. Willebrand disease
 - Psychoactive substance dependency (Active injection drug use, Inhalate cocaine, Marijuana/ cannabis, Opiate substitution)
 - Other

The patient's alcohol consumption will be displayed in a further table, i.e.:

- Alcohol use (None, Yes – occasional, Yes – regular, Ex-drinker [6 units/drinks per day, none in the last 3 months])
- Average number of units/drinks per week (if regular alcohol use is reported)

One unit/drink is defined as 10 milliliters (or approximately 8 grams) of pure alcohol and equals: 200 ml of beer or 100 ml of wine or 20 ml of hard liquor. An overview of Tables and Listings for the above mentioned variables is given in Table 7.

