4.2.8.4 Laboratory Data

All reported clinical laboratory test results will be assigned to one of the time points using the time windows specified in the Table 4. All will be performed for the SP by treatment regimen and cirrhosis status.

Changes from baseline to each post-baseline visit will be summarized descriptively (N, mean, SD, median, minimum, maximum). A summary table will show laboratory hematology. In another table information about clinical chemistry

In a further table CD4 and HIV-RNA are displayed for patients with HIV only by visit. A further table will show the viral resistance.

Instead of the shift tables mentioned in the study protocol, the number and percentage of subjects with post-baseline values until EoT meeting the specified criteria for Potentially Clinically Significant (PCS) laboratory values (defined in Table 10) will be summarized. A post-baseline value must be more extreme than the baseline value to be considered a PCS finding.

Table 10 Criteria for PCS laboratory values

Laboratory data	Very Low	Very High
Laboratory hematology		
Hemoglobin [g/L]	<80	
Platelets [10^9 /L]	<50	
Laboratory clinical chemistry		
ALT		>5 x ULN and >= 2 x baseline
AST		>5 x ULN and >= 2 x baseline
Creatinine [$\mu\text{mol}/\text{L}$]		>132.605
Creatinine clearance [mL/min]***	<50	

*** estimated by Cockcroft-Gault-Formula (see above)

Additionally, for hemoglobin and creatinine clearance, the number and percentage of subjects with a maximum Common Terminology Criteria for Adverse Events (CTCAE) Grade of 0, 1, 2, 3, or 4 (see definitions in Table 11) at any post-baseline visit (regardless of the baseline value) through the end of treatment (i.e., Final Treatment Value) will be summarized. For the liver function tests (LFTs) of ALT and AST, the number and percentage of subjects in with a maximum CTCAE Grade of 0, 1, 2, 3, or 4 (see definitions in Table 11) at any post-nadir visit through the end of treatment (i.e., Final Treatment Value) will be summarized. Note, for these analyses, the nadir is used for reference (including baseline).

Table 11 Definition of CTCAE Grades 0-4

Laboratory data	Grade 0	Grade 1	Grade 2	Grade 3	Grade 4
ALT	<=ULN	>ULN – 3 x ULN	> 3 – 5 x ULN	> 5 – 20 x ULN	> 20 x ULN
AST	<=ULN	>ULN – 3 x ULN	> 3 – 5 x ULN	> 5 – 20 x ULN	> 20 x ULN
Hemoglobin Decreased [g/L]	>=130	<130 – 100	< 100 - 80	< 80 - 65	< 65

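### The SAP's laboratory safety tables do not separate new from pre-existing hemoglobin, platelet and renal abnormalities

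*SAP*

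**What the plan says.** Protocol 9.7.4 (text below Table 4) planned to count patients with "shifts during treatment in clinical laboratory values from low/normal to high and high/normal to low based on the reference range". SAP 4.2.8.4 states openly that it replaces these shift tables. It sets out two kinds of count for the safety population, by treatment regimen and cirrhosis status.

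- **PCS values (Table 10).** The limits are hemoglobin below 80 g/L, platelets below 50 x 10^9/L, creatinine above 132.605 µmol/L and creatinine clearance below 50 mL/min. For these four the only reference to baseline is the general rule: "A post-baseline value must be more extreme than the baseline value to be considered a PCS finding". For ALT and AST the criterion itself refers to baseline: ">5 x ULN and >= 2 x baseline".
- **Worst CTCAE grade (Table 11).** For hemoglobin and creatinine clearance the maximum grade is taken "at any post-baseline visit (regardless of the baseline value) through the end of treatment". For ALT and AST only values after the nadir count, and "for these analyses, the nadir is used for reference (including baseline").

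Other planned outputs bear on the point. SAP 4.2.8.4 summarizes changes from baseline by visit. SAP 4.2.6.5 groups baseline creatinine clearance into Grades 1 to 4 and reports baseline hemoglobin and platelets without grading. SAP 4.2.6.4 lists among the co-morbidities "Chronic kidney disease (Mild, Moderate, Severe, Currently on dialysis, Currently not on dialysis").

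**The concern.** There is no untreated comparator, so a laboratory abnormality seen on treatment can be read as new only against the patient's own baseline. A shift table makes that comparison patient by patient. The two replacement counts do not make it for the grade table. For the PCS table they make it only in the weak sense that one later value must be worse than baseline by any amount.

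The plan is stricter elsewhere. ALT and AST have a twofold condition and a nadir reference, and SAP 4.2.8.3 counts adverse events as treatment-emergent, in the main, only if they start or get worse after the first dose. No reason is given for treating hemoglobin, platelets, creatinine and clearance differently.

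At stake is how the renal and hematology tables are read. Protocol 7.1 attributes many laboratory abnormalities to ribavirin, so readers will compare columns with and without it. Regimen is tied to disease: under SAP 4.2.1, cirrhotic genotype 1a patients and all genotype 4 patients are outside the core population unless they receive ribavirin. Columns may therefore differ at baseline, and these two tables would not show how much of a difference was already there.

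**Working it through.** The plan states no rate or target for these tables, so there is no figure to reproduce. The check applies the SAP rules to example patients and then works out how often a stable patient is flagged.

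**1. Grade table, using the Table 11 limits.**
- Clearance 45 mL/min before and during treatment: counted as Grade 2.
- Clearance rising from 20 to 25 mL/min: counted as Grade 3 despite the improvement.
- Hemoglobin anywhere from 100 to just under 130 g/L before and throughout treatment: counted as Grade 1.

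**2. PCS table, using the Table 10 limits.**

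| Value | Baseline | Worst on treatment | PCS? |
|---|---|---|---|
| Clearance, mL/min | 45 | 45 | No |
| Clearance, mL/min | 45 | 44.9 | Yes |
| Platelets, 10^9/L | 45 | 48 | No |
| Platelets, 10^9/L | 45 | 44 | Yes |
| Platelets, 10^9/L | 60 | 49 | Yes |
| ALT (ULN 40 assumed) | 210 | 211 | No, below 2 x baseline |

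Platelets falling from 45 to 44 and from 60 to 49 enter the same count, although only the second patient has crossed the limit.

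**3. Chance that a stable patient is flagged.** Take a patient well beyond a limit, with no drug effect and k on-treatment values. The baseline and the k later values are exchangeable, so baseline is the most extreme of the k+1 values with probability 1/(k+1). At least one later value is more extreme with probability

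1 − 1/(k+1) = k/(k+1).

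- k = 1: 1/2 = 50%
- k = 2: 2/3 = 67%
- k = 3: 3/4 = 75%
- k = 5: 5/6 = 83%

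The documents do not fix k, because sampling follows routine practice. For a 12-week regimen, the visit schedules in Protocol Annexes 3 and 4 suggest one early on-treatment visit plus end of treatment, so k of about 2. The windows in SAP Table 4 allow 3 or more if values are recorded.

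Closer to the limit the chance is lower, because a baseline that falls beyond the limit is then more likely to be an extreme draw. Simulation with true clearance 35 to 45 mL/min and within-patient CV of 8% to 12% (both assumed) gives about 60–67% for k = 2 and 69–75% for k = 3.

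**4. Share of the PCS count.** This needs the baseline distribution, which the documents do not give. Purely as illustration, assume platelets with median 110 and log-SD 0.5, clearance with median 95 and log-SD 0.35, CV 5–15%, k from 3 to 5 and no drug effect. Then 50–79% of patients already below the limit are flagged, and they make up 32–77% of all PCS cases. The width of that range shows how little can be said without data.

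**5. Can other outputs recover the split?**
- Change summaries give mean, SD, median and range for a group. They do not count patients who crossed a limit or a grade.
- Baseline clearance grades are shown for the safety population in the same columns. Equal counts at baseline and at worst fit both no one changing and as many worsening as improving.
- Grades 0 and 1 may not line up. The baseline table uses the laboratory's lower limit of normal, with 75 mL/min only if that is missing, while Table 11 always uses 75.
- Hemoglobin has no baseline grades, so not even that marginal comparison is possible.
- SAP Table 12 lists no output by baseline grade.

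**The case against.** The strongest reply is that baseline is not ignored. Changes from baseline are summarized by regimen and cirrhosis status. Baseline clearance grades and kidney co-morbidities are tabulated in the same columns. The cirrhosis split removes part of the case-mix difference. The PCS rule does require worsening, so a stable patient whose later values never pass baseline is not counted. The output whose title fits the grade counts is Worst Laboratory Values, which does not claim that the findings are new. The layouts are in SAP Part II, which is not among the documents, so a baseline column there cannot be excluded. All of this stands and lowers the severity. It does not supply a patient-level link in the text.

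A reader might infer more than the documents support:

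- *That the tables mostly show baseline case mix, or will look like ribavirin toxicity.* No prevalence of baseline abnormality is given, and the change tables are free of this problem.
- *That dialysis patients will certainly be present.* The co-morbidity list is a set of form categories and does not show who enrols; eligibility follows a label that the documents do not reproduce.
- *That all pre-existing low platelets are reported as on-treatment findings.* Platelets are not in Table 11, and the PCS rule needs at least one lower value.
- *That patients already beyond a limit should be removed from the PCS count.* That would also hide real deterioration, such as platelets falling from 48 to 15. The protocol's shift tables miss such patients too, so they are no ideal standard.

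**Conclusion.** The point holds as a limited one. As the SAP text stands, the worst-grade counts for hemoglobin and creatinine clearance, and the PCS counts for hemoglobin, platelets, creatinine and creatinine clearance, mix new abnormalities with existing ones. Nothing described in the text separates them by patient.

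For a stable patient already well beyond a PCS limit, the chance of being flagged is about k/(k+1): 67% for k = 2 and 75% for k = 3. This assumes exchangeable values and no drug effect, and k itself is assumed. It applies only to such patients, whose number is unknown, so the effect on the tables as a whole cannot be sized. The PCS part matters least for hemoglobin if, as seems likely, few patients start below 80 g/L.

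The tables are descriptive safety outputs and the SVR12 analysis is untouched. Severity is minor.

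**What to change.** 1. In the Worst Laboratory Values table, cross-tabulate maximum post-baseline grade by baseline grade for hemoglobin and creatinine clearance. Apply the Table 11 limits at both times, and give the number of patients whose grade rose by at least one.
2. In the PCS table, keep the current rule. For hemoglobin, platelets, creatinine and creatinine clearance, split each count into patients already beyond the limit at baseline and patients who were not. Worsening in the first group then stays visible.

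Both changes use values already collected and need only SAP wording and table shells. The cost is a larger table with some sparse cells. If SAP Part II already contains such a layout, a sentence in 4.2.8.4 saying so is enough.

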4.2.9 Interim Analyses

In contrast to the study protocol one interim analysis was performed as soon as the first 100 patients could have reached the SVR12 time point and the data are sufficiently cleaned (instead of as soon as the first 200 patients finished the study).

Site information and researcher experience were displayed, as well as patient disposition by genotype and cirrhosis status for the EP.

For all patients in the CP the following baseline tables were created:

- treatment regimen
- socio-demographic characteristics
- CHC disease characteristics
- CHC Related laboratory variables at baseline
- other key laboratory variables at baseline
- CHC treatment history in treatment experienced patients
- Co-morbidities and co-infections
- alcohol consumption
- CD4 and HIV-RNA in patients with HIV at baseline

Additionally, the CP will be restricted to the patients who could have reached SVR12 time point (i.e. patients with planned treatment duration 12 weeks and DAA treatment start before 01APR2016). The baseline analyses mentioned above and patient disposition were repeated and in addition the following tables will be created:

- Premature termination of treatment and its main reason
- Virological response rates

Non-response rates were displayed for the CPSFU12. All tables were structured by genotype and cirrhosis status.

The SP was restricted to patients who could have reached SVR12 time point (i.e. patients with planned treatment duration 12 weeks and DAA treatment start before 01APR2016). The following tables will be created for the SP

- Treatment-emergent AEs
- Serious Treatment-emergent AEs

All tables were structured by treatment regimen and cirrhosis status.

4.2.10 Protocol Violations and Deviations

Enrolled patients who are excluded from the analysis populations will be summarized and the reasons listed (see section 4.2.1).

5. DATA QUALITY ASSURANCE

Data for this study will be recorded in English by each participating center via an electronic data capture (EDC) system using a web-based eCRF.

A comprehensive data validation program utilizing front-end checks in the eCRF will validate the data. Automated checks for data consistency will be implemented, discrepancies need to be solved by the researcher in the eCRF before the module can be completed.

Follow-up on eCRF data for medical plausibility will be done by AbbVie personnel (or their representatives). Queries will be generated in the eCRF for online resolution at the site. The investigator or an authorized member of the investigator's staff will make any necessary data corrections to the eCRF. All change information, including the date and person performing the corrections, will be available via the audit trail, which is part of the EDC system. The principal investigator of each site will finally review the eCRFs for

completeness and accuracy of available data and provide his or her electronic signature and date to the eCRFs as evidence thereof.

All statistical programs employed in the analysis and reporting of the data will be validated according the standard operating procedures of IST and results will be checked for plausibility.

6. METHODS OF DATA ANALYSIS AND PRESENTATION

All statistical analyses will be carried out by means of the SAS® package (Version 9.4).

6.1 Analysis Data Sets

A value added dataset STRATIFY will be programmed. This will contain derived variables, e.g. analysis populations, treatment regimen and relevant baseline characteristics, needed for the generation of the planned analyses.

A value added dataset SITES will be programmed. This will contain site information and researcher experience needed for the generation of the planned analyses.

Additional value added dataset will be programmed for the primary and secondary endpoints.

6.2 SAS Output Format

Detailed descriptions of the SAS outputs are given in Part II of the SAP (Table Shells).

